12. OTHER STUDY ADMINISTRATION CONSIDERATIONS

12.1 Concomitant use of medications or interventions during the course of the study

All relevant concomitant care and interventions are permitted throughout the study.

12.2 Allocation sequence generation and concealment mechanism

To randomize participant group assignment, an online program called QMinim (<http://rct.mui.ac.ir/qminim/>) will be utilized. This program uses a process called minimization which ensures group sizes are equal and eliminates potential bias that may be introduced which is important for clinical research of small sizes (BMJ 2005;330:843).

12.3 Blinding Procedures

Participants will not be blinded to his/her group assignment. Participants placed into the SC group will be given the option of receiving the AET after completion of the study, although this will not be included in data analysis.

[name], [name], [name], and [name] will be blinded from group assignment for data analysis purposes.

12.4 Premature discontinuation or termination of the study

The study sponsor/investigator and the Research Ethics Board reserve the right to terminate this research study at any time. Reasons for termination include but are not limited to:

The occurrence of adverse events poses a potential health risk for participants;

Unsatisfactory participant enrollment;

Investigator request to withdraw from study;

Noncompliance with the protocol or regulatory guidelines are not being followed;

REB decision to terminate or suspend approval for the investigation or Investigator.

12.5 Ancillary and post-trial care

Participation in this study is not expected to cause any harm, and the participant can withdraw at any time. There is no compensation as the participant agrees to the risks outlined in the information letter.

13. QUALITY CONTROL AND QUALITY ASSURANCE

We are able to track adherence to the protocol because the intervention requires a visit which is documented in the data abstraction form. All data will be translated into the data abstraction forms. To promote data quality, all team members will be trained in their duties. All questionnaires to be used are valid (see Section 7.2).

13.1 Data Integrity Measures

See above. All members of the research team are responsible for adhering to the protocol and ensuring data quality.

13.2 Training Study Staff

All members of the research team will be protocol trained. All duties to be performed by members of the research team will be delegated by the Principal Investigator. Appropriate task training will be completed by the PI/research team prior to the study start. All supervisors for the AET program will be certified by the Canadian Society for Exercise Physiology. The NOSM research assistant is TCPS 2 CORE trained in order to administer informed consent. [name] will supervise the NOSM research assistant who is already trained in all protocols covering the roles of saliva analysis and group assignment.

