6.4 Procedures for Participant Enrolment /Allocation /Randomization

To achieve adequate enrolment, recruitment flyers will be placed at several locations and clinics around Thunder Bay. Once informed consent has been obtained, and the potential participant has been deemed eligible through the screening process, age and sex of the participant will be used to randomly assign the participant to an intervention group through a process called minimization. This process ensures group sizes are equal and eliminates potential bias that may be introduced which is important for clinical research of small sizes. The NOSM research assistant would then communicate the enrolment and group assignment to [name] who will administer the AET intervention. The SC intervention will continue under the supervision of the participant's healthcare provider. Participants will be assigned a code number by the research assistant to ensure confidentiality is maintained during the transfer of data or samples between locations.

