8.2 Data Management

The research team (Principal Investigator, Co-Investigators and research assistant) has access to all data if necessary. The research assistant will create a code key that will be kept on a secure Sync.com account (see below for further information, access provided through NOSM) in an encrypted file, along with the electronic coded data abstraction files. These files will be kept separate from the code key in order to prevent participant identification.

The hard copy screening checklists will be coded and stored in [name] current office in a locked filing cabinet at School of Kinesiology, Lakehead University (SB-1007). Electronic copies will be uploaded to the secure Sync.com account.

Saliva samples will be immediately coded and processed/stored in the NOSM laboratory. Results of the saliva analysis will be stored in an encrypted file on a password protected computer in a secure office.

[name] will extract ImPACT data from the ImPACT Applications, Inc. server to a password protected computer in a secure office. Electronic data collected from the BESS will be transferred to a secure USB (for data transfer) and then to a password protected computer in a secure office. All paper and electronic data will be coded and uploaded to the secure Sync.com account.

Electronic data collected from the Oddball and Flanker tasks will be coded to a secure USB (for data transfer) and transferred to a password protected computer in a secure office. Data will then be uploaded to the secure Sync.com account.

Electronic Data collected from the driving simulation will be coded and transferred to a secure USB (for data transfer) and then to a password protected computer in a secure office. Data will then be uploaded to the secure Sync.com account.

Sync.com account details:

The website states the following:

Sync's unique, zero-knowledge storage platform guarantees your privacy by providing end-to-end encryption, and most importantly - only you have access to the encryption keys. We can't read your files. Neither can the NSA.

- Zero-knowledge, end-to-end encryption
- Privacy guarantee (we can't access your files or file metadata)
- 2048 bit RSA, 256 bit AES, SSL and TLS encryption
- Files encrypted in transit and at rest
- Share controls, permissions and user administration
- Remote logout

- Remote wipe
- File audit logs
- Account notifications
- Two-factor authentication

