9. SPECIMEN MANAGEMENT

A research assistant, will facilitate the collection of the saliva following an establish passive drool protocol. Participants will be instructed to drool through a straw into a collection tube. The samples will be transported Lakehead University School of Kinesiology to NOSM for processing and analysis. Salivary BDNF will be quantified using an established protocol in [name] lab, which utilizes an enzyme-linked immunosorbent assay. All samples will be labeled with the participant code number as well as a letter for each time point. For example, A for pre-treatment, B for post-treatment. Samples will be kept until all analysis is completed, after which all labels will be removed and samples will be disposed of as biohazardous waste.

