10. DATA / SPECIMEN ANALYSIS

[name] and the NOSM research assistant will be performing data analysis on the saliva samples at NOSM. [name], [name], [name], and [name] will be performing analysis on the physical and cognitive measures at Lakehead University. The main analysis will be a comparison of the pre- and post-outcomes.

[name] will perform the analysis of the data collected related to balance from the AMTI force platform and ImPACT neurocognitive assessment. The AMTI force platform measures the ground reaction forces that are generated by a body standing or moving across the plate. The AMTI force plate is also capable of measuring torques about each axis and has six degrees of freedom, which includes three forces (f_z , f_x , and f_y) and three moments (M_z , M_x , and M_y). All of these measures are fed into an AMTI amplifier and converted to digital signals via an analog to digital converter. The information collected by the force platform is then uploaded into BIOSOFT computer software which allows the researcher to view and analyze data following collection. The BIOSOFT computer software calculates the x and y moments of postural sway which are used to compute the variables of interest and produces graphical representations of this data. Descriptive statistics will be calculated to provide the mean and standard deviations for the variables of interest including the area of the centre of pressure, velocity of centre of pressure, length of centre of pressure, and displacement of centre of pressure. The main objective of the analysis is to compare pre- and post-treatment changes in balance. The ImPACT measures components of cognitive functioning including: attention, concentration, reaction time, memory, processing speed, decision making, problem solving, and response variability. The main objective of this component of the analysis will be to compare pre- and post-treatment changes in composite scores for the variables described.

[name] will perform the analysis on the data collected from the driving simulator. This analysis will include the comparison of people with concussion who will undergo AET to those

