14. REGULATORY CONSIDERATIONS

14.1 Participant privacy and confidentiality

Data will be kept confidential throughout the study through the following measures:

- a key will be created with a list of participant names and their respective codes, in a password protected encrypted document on a secure computer at Lakehead University. This computer will remain in a locked cabinet in a locked office except when in use at one of the research sites, as well as when in transport between sites. Only the research team will have access to the key.
- The key will be kept in a separate file (using a different password) from all original raw data,
- To ensure participant data can be immediately coded following collection, the key will be placed in an encrypted folder in a secure Sync account, (see below for more details) to which only research team members will have access.
- Saliva samples will be coded immediately following the draw
- All data abstraction forms and screening tools will be coded and abstraction forms will only be electronic (saved into password protected folders on secure Sync account),
- No data will leave the collection site uncoded, -Only members of the research team will have access to the data,
- Data will be stored in secure offices on password protected computers at the location they were collected,
- All data published will use aggregate data so no individual person can be identified.

The data will not be disclosed to third parties, and original signed consent forms/coded screening tools will stay in secure filing cabinets in [name] secure office at the Lakehead University School of Kinesiology (currently number SB 1007). All data will be kept for a minimum of five years, after which it will be destroyed. Any data collected during the screening process (signed consent forms, screening checklists) for a potential participant who does not meet the criteria, and who will therefore not be included in the study, will be securely destroyed in a locked Enviroshred box for confidential shredding.

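### The research assistant who handles group assignment and issues participant codes also runs the BDNF assay on tubes carrying that code and a pre/post letter, and no assay masking is described

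*Combined protocol and SAP*

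**What the plan says.** The relevant duties are spread over several sections of the combined protocol and SAP.

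- **Allocation.** Section 6.4: "The NOSM research assistant would then communicate the enrolment and group assignment" to the person who delivers the exercise programme. Section 13.2 describes the same assistant as "already trained in all protocols covering the roles of saliva analysis and group assignment". The allocation itself is generated by the minimization program named in 12.2.
- **Participant codes.** Section 6.4: "Participants will be assigned a code number by the research assistant". The stated purpose is confidentiality.
- **Tubes.** Under 8.1 the research assistant labels each tube with the participant code and takes it to NOSM. Section 9 adds: "All samples will be labeled with the participant code number as well as a letter for each time point". A stands for pre-treatment and B for post-treatment.
- **Assay.** Note 3 to the budget in 16.6 puts the ELISA and the organisation of the study arms in one 0.25 FTE research assistant post.
- **Saliva data.** Section 10 states that a team member (name removed) and "the NOSM research assistant will be performing data analysis on the saliva samples at NOSM".
- **Blinding.** Section 12.3 says participants are not blinded and that four people (names removed) are blinded to group for data analysis. It does not mention the assay.
- **Use of the result.** BDNF is the subject of the secondary objective (section 2) and one of the four outcome types in the group-by-time ANOVA of 11.2.

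**The concern.** Section 1 gives heavy reliance on self-report as a possible reason why earlier treatment studies failed, and brings in objective measures, BDNF among them, in response. Because participants know their group, masking in the laboratory is one of the few protections left for this outcome. The plan's own division of work removes it for the assay operator: the tube label tells the person who issued the code which participant the sample came from, that person has handled the participant's allocation, and the letter gives the time point. Any discretionary step in the assay could then be influenced, without intent, by the expectation stated in 11.2 of greater change in the exercise group. The AET–SC contrast in BDNF change is at stake. If no interaction is found, so is the main effect of time that 11.2 then examines.

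**Working it through.** The plan states no figure to reproduce on this point. The check traces one post through the steps and asks whether any step hides arm or time point from the assay operator.

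**Step 1: is it one person?** Sections 6.4 (allocation), 10 and 13.2 name the NOSM research assistant. The code-issue sentence in 6.4, section 8.1 and the budget say only research assistant. The budget funds a single 0.25 FTE research assistant, whose listed duties include saliva collection, transport, the ELISA and organising the arms. Reading these as the same person is an inference, but the natural one.

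**Step 2: what does the operator know?**

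| Item | Known through | Section |
|---|---|---|
| Arm of each participant | handles and passes on the assignment | 6.4, 13.2 |
| Code of each participant | issues it | 6.4 |
| Which participant a tube belongs to | code on the label | 8.1, 9 |
| Time point | letter on the label | 9 |

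Code to participant, and participant to arm, are both known to the same person. No section describes a separate laboratory number that would break this chain.

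**Step 3: where is there room for choice?** Section 7.2 (Biomarker Assessment) fixes the reagents, the timed stop, the reading at 450 nm, duplicate wells, standards from 15.63 to 500 pg/ml and the regression used for concentrations. It gives no rule for plate layout, for repeating or discarding discordant duplicates, or for values outside the standard range.

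**Step 4: does plate layout matter?** It does if more than one plate is needed.

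- Samples: 60 participants × 2 time points = 120; in duplicate, 240 wells.
- Assumption: six two-fold standards (15.63, 31.25, 62.5, 125, 250 and 500 pg/ml) and one blank, all in duplicate, use 7 × 2 = 14 wells per plate.
- Wells left: 96 − 14 = 82, which is 41 samples. Without the blank, 96 − 12 = 84, which is 42 samples.
- Plates: 120 / 41 = 2.9 or 120 / 42 = 2.9, so three either way.

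With three plates, arm or time point could be partly confounded with plate, and the protocol leaves the layout open to someone who may know both. Whole pairs also fit: 20 pairs need 20 × 2 × 2 = 80 wells, 80 + 14 = 94 of 96, and 3 × 20 = 60 pairs. Repeats would then need a further plate.

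**The case against.** The strongest reply is that an ELISA leaves little to the operator. The plate is read by an instrument, samples run in duplicate, and 7.2 says how concentrations are derived. A reader might infer that the standard curve is another point of discretion; 7.2 does not support that, since it refers to a regression equation supplied with the standards. This reply stands as far as it goes, and it is why the likely bias is modest. It does not cover the steps on which 7.2 is silent.

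A reader might also infer that every sample is in fact read with the arm in view. The documents do not say so. No arm list at the bench is described, and samples are stored until collection is complete, so the operator would have to recall or look up the arm behind up to 60 codes. What the documents do show is that nothing prevents it.

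Nor should the code key carry the argument. Section 8.2 has the research assistant create it, but 14.1 describes a list of names and codes, not groups, and opens it to the whole team: "Only the research team will have access to the key". The chain in the working does not need the key.

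The time letter alone cannot produce a difference between arms; it matters together with knowledge of arm, or for the main effect of time. The planned correlation of entry BDNF with symptoms is not an arm comparison and is less exposed.

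Finally, the co-analyst in section 10 may be one of the four blinded people in 12.3. The removed names leave this open. A blinded co-analyst would protect the data analysis, but would not mask the person running the plates.

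**Conclusion.** The point holds as a gap in masking. As the duties are written, coding does not conceal arm or time point from the person who runs the BDNF assay, and 12.3 describes no other safeguard for it.

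The size cannot be derived from the documents. They give no assay variability, repeat rate or rate of out-of-range values. A reader might want to translate the gap into an inflated false-positive rate for the AET–SC comparison, but any such figure would rest entirely on an assumed shift. The supportable statement is that the bias is probably modest, with plate layout, repeats, discarded duplicates and out-of-range wells as its routes.

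Two assumptions remain: that the research assistant in 6.4, 8.1 and the budget is the NOSM assistant of 10 and 13.2, and that this person is not among the removed names in 12.3. Being listed there as blinded would conflict with 6.4 and 13.2. This is a cheap improvement to make before the assay is run, not a flaw that undermines the trial.

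**What to change.** Use the storage step already in 7.2. Once the last sample is in:

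1. An existing team member who neither runs the assay nor analyses outcomes relabels all 120 aliquots with random IDs that show neither participant code nor time point. The graduate student is not an obvious choice, since budget note 2 includes data interpretation among that role's duties.
2. The same person places each participant's two samples on one plate and allocates pairs to plates at random. Random allocation needs no arm list, so nobody further is unblinded.
3. Rules for repeats, discordant duplicates, exclusions and values outside the standard range are written down before the first plate is run.
4. The link from random ID to participant and time point is released only after the concentrations are locked.
5. Sections 9 and 12.3 state, by role, that the assay operator is masked to arm and time point, and whether the saliva co-analyst is blinded.

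The cost is a few hours of relabelling, a short edit to two sections and a small risk of labelling error, which a second check of the list would reduce. Sample size and participant procedures do not change, and no new staff are needed.

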13.3 Auditing and Monitoring

There is no auditing conduct.

14. REGULATORY CONSIDERATIONS

14.1 Participant privacy and confidentiality

Data will be kept confidential throughout the study through the following measures:

- a key will be created with a list of participant names and their respective codes, in a password protected encrypted document on a secure computer at Lakehead University. This computer will remain in a locked cabinet in a locked office except when in use at one of the research sites, as well as when in transport between sites. Only the research team will have access to the key.
- The key will be kept in a separate file (using a different password) from all original raw data,
- To ensure participant data can be immediately coded following collection, the key will be placed in an encrypted folder in a secure Sync account, (see below for more details) to which only research team members will have access.
- Saliva samples will be coded immediately following the draw
- All data abstraction forms and screening tools will be coded and abstraction forms will only be electronic (saved into password protected folders on secure Sync account),
- No data will leave the collection site uncoded, -Only members of the research team will have access to the data,
- Data will be stored in secure offices on password protected computers at the location they were collected,
- All data published will use aggregate data so no individual person can be identified.

The data will not be disclosed to third parties, and original signed consent forms/coded screening tools will stay in secure filing cabinets in [name] secure office at the Lakehead University School of Kinesiology (currently number SB 1007). All data will be kept for a minimum of five years, after which it will be destroyed. Any data collected during the screening process (signed consent forms, screening checklists) for a potential participant who does not meet the criteria, and who will therefore not be included in the study, will be securely destroyed in a locked Enviroshred box for confidential shredding.

14.2 Ethical Review

It is the understanding of the sponsor that this protocol as well as appropriate consent procedures will be reviewed and approved by the Thunder Bay Regional Health Science Centre. This board operate in accordance with the current Canadian Regulations. Approval from the board will be obtained before starting the study, and will be documented in a letter to the investigator specifying the date on which the board met and granted the approval. All protocol modifications will be reviewed and approved by the appropriate Research Ethics Boards in accordance with local requirements, before the changes can be implemented. Modifications which eliminate an apparent immediate hazard to participants do not require pre-approval by the Research Ethics Board. Such deviations will be recorded and explained in the annual REB report.

14.3 Scientific Review

The Northern Ontario Academic Medical Association has reviewed this study.

14.4 Institutional Review

This protocol as well as required resources will be reviewed and approved by the Thunder Bay Regional Health Sciences Centre Research Program. Approval must be obtained prior to initiating the study.

14.5 Clinical Trial Registration

This study will be registered as a clinical trial at ClinicalTrials.gov

14.6 Retention of Study Documents

All original signed consent forms and screening checklists will be maintained confidentially at Lakehead University School of Kinesiology in a locked filing cabinet in [name] secure office (currently SB-1007). To protect participant data, each participant will be given a code. A code key will be created in a password-protected and encrypted file away from raw data. This key will also be placed on the secure Sync.com account. All data abstraction forms will be electronic and coded. They will be stored in an encrypted file on the Sync.com account.. All data will be kept for a minimum of 5 years after which it will be destroyed securely.

